## **3.0 STUDY DESIGN**

This is a prospective, single institution, controlled, pilot study of patients admitted to the 7W ICU which will compare the incidence and delirium rates among patients undergoing routine care before

intervention (no routine psychiatric involvement) (control group) and patients after the intervention (psychiatry team rounding with the ICU team daily) (intervention group) . Randomization is not possible for this study; although block randomization was considered, it will result in sub-optimal data subject to bias.

A sample size of 104 (52 per group) is targeted based on an *a priori* sample size calculation. Patients will be screened on a daily basis for study eligibility by study personnel and ICU team members, before delirium develops. Patients in both groups will be given an information sheet, verbal consent will be obtained, and the patient's agreement to participate will be documented in the medical record. For patients who are unable to make their own decisions, the information sheet will be given to their designated healthcare decision maker, verbal consent will be obtained, and the healthcare decision maker's agreement will be documented in the medical record.

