The control group will receive standard care, including the use of the ABCDEF bundle (Appendix 1) daily, which involves delirium screening using the Confusion Assessment Method-Intensive Care Unit (CAM-ICU) score (Appendix 2), but will not have routine psychiatric involvement in care. The CAM-ICU is performed by the ICU nurses on a daily basis. It consists of several questions that assess patient's mental status, if the change in mental status fluctuates, the sedation score (using Richmond Agitation Sedation Score [RASS]), and the patient's attention span and if disorganized thinking is present by asking several questions. The CAM-ICU can be performed in intubated patients by asking the patient to follow commands with their hands, or squeeze the nurse's hand in response to a question. The CAM-ICU will be done every morning, but may also be repeated later on in the day if the patient's mental status changes from the morning-this will be the same for both the control and intervention group. Enrollment and data collection will continue for as long as it takes to reach the target sample size of 52 patients for this group. We will then provide standard care (including ABCDEF bundle implementation, which is standard practice in 7W ICU) and provide routine psychiatric care, which entails a member of the psychiatric team (attending, resident, and/or fellow) participating in daily (Monday-Friday) multidisciplinary rounds with the ICU team (intervention group); the psychiatry team will help provide nonpharmacological and pharmacological intervention strategies in patients diagnosed with delirium and help distinguish delirium from other psychiatric disorders which may be missed by the ICU team and provide earlier treatment of these conditions. This study phase will continue until the target sample size of 52 patients is reached.

In both the control and intervention groups, delirium will be diagnosed by a positive CAM-ICU score. Both groups will have the CAM-ICU test administered by the patient's nurse on a daily basis (which is standard practice in 7W ICU) in the morning and may be repeated later on in the day if the patient's mental status changes. Data on the incidence of ICU delirium, duration of delirium/mechanical ventilation, in-house mortality, hospital and ICU length of stay will be collected.

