## **6.0 STRATIFICATION/DESCRIPTIVE FACTORS/RANDOMIZATION SCHEME**

This is a prospective, single institution, controlled, pilot study of patients admitted to the 7W ICU. A sample size of 104 (52 per group) is targeted. Patients will be screened for study eligibility on a daily basis. The control group will undergo standard ICU care, which includes the use of the ABCDEF bundle (Appendix 1) daily, which involves delirium screening using the CAM-ICU tool (Appendix 2), but will not have routine psychiatric involvement in care. Enrollment and data collection will continue for as long as it takes to reach the target sample size of 52 patients for this group. We will then proceed to enroll patients into the intervention group, who undergo standard care (including ABCDEF bundle implementation, which is standard practice in 7W ICU) in addition to a psychiatric team intervention, which entails having a member of the psychiatric team (attending, resident, and/or fellow) participate in daily (Monday-Friday) multidisciplinary rounds with the ICU team; they will help provide nonpharmacological and pharmacological intervention strategies in patients diagnosed with delirium and help distinguish delirium from other psychiatric disorders which may be missed by the ICU team and provide earlier treatment of these conditions. This study phase will continue until the target sample size of 52 patients is reached.

Data will be collected for both the control and intervention groups (see Section 12) and compared.

Randomization is not possible for this study; although block randomization was considered, it will result in sub-optimal data subject to bias.

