## **12. DATA COLLECTION AND MONITORING**

Data which will be collected includes: age, gender, body mass index, history or alcohol or substance abuse, admitting diagnosis, dementia, comorbid conditions, admitting Sequential Organ Failure Assessment (SOFA) score, deliriogenic medications used during study enrollment, the interventions/medications used to treat delirium as designated by psychiatry in conjunction with the ICU team (in intervention group) and the ICU team (control group), and the number of days from ICU admission to study enrollment. Data on the incidence of ICU delirium, duration of delirium/mechanical ventilation, in-house mortality, and length of stay will also be collected.

Data will be collected using RedCap, a password protected website. No patient identifiers will be used. A copy of the information sheet will be provided to the patient and be placed in the patient's chart. We will retain a copy of the information sheet in a double locked storage office.

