## **13.0 STATISTICAL CONSIDERATIONS**

In this pilot study, sample size considerations were based on obtaining sufficient patient numbers to assess feasibility of the intervention and data collection on the surgical unit, as well as to obtain estimates of incidence of delirium in the current care model (the base incidence) and the magnitude of effect of introduction of psychiatric involvement on the unit. All of these data are required for determination of feasibility of and sample size estimation for a larger definitive trial that would likely be a multi-centered cluster randomized trial. Based on our clinical experience in the 7W ICU, the incidence of delirium over the past year was roughly 40%; from the literature, a large intervention effect would be on the order of 25% reduction in incident delirium. We used these initial approximations to determine the precision (i.e., width of a 95% confidence interval) with which we can estimate these two parameters for use in future trial planning. Given a sample size of 94 patients (47 in each group), we will be able to estimate the actual difference in the incidence of delirium in our proposed intervention group (compared to SOC) with a precision (95% confidence interval) of 8%-42%. In the 47 in the SOC group, we will be able to estimate the base rate of delirium incidence with a 95% confidence interval of 26%-55%. The effect size and base rate estimated from this pilot trial will help us design future multi-center, larger population studies.

A sample size of 104 will be targeted to account for a 10% drop-out rate.

Descriptive statistics, including Student's t-test or Mann-Whitney U-test, for continuous variables and  $\chi^2$  or Fisher's exact test, for categorical variables, will be used to summarize the data and compare

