characteristics between the 2 groups. The incidence of delirium will be compared using  $\chi^2$  test and multivariable logistic regression. Differences in the duration of delirium and MV between the intervention and control groups will be analyzed by analysis of variance (ANOVA). The length of stay will be compared by truncated negative binomial regression, while mortality rates will be compared via logistic regression. A sensitivity analysis will be performed in order to assess the possible confounding effect of the non-randomized nature of our study design. A propensity score model for receipt of standard care vs. psychiatric involvement will be performed in order to approximate a balanced covariate distribution between the 2 groups as that would be expected by randomization. We will then use the propensity score for each subject to perform an inverse probability weighted comparison of the groups on our trial outcomes.

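### The planned adjustments cover measured case mix only and cannot assess confounding by calendar time, which in this before-after design fully determines group

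*Combined protocol and SAP*

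**What the plan says.** Section 3.0 describes a single-institution comparison of patients before and after psychiatry joins ICU rounds. It rules out random allocation: "Randomization is not possible for this study; although block randomization was considered, it will result in sub-optimal data subject to bias". Controls come first: "Enrollment and data collection will continue for as long as it takes to reach the target sample size of 52 patients for this group". Section 6.0 then continues: "We will then proceed to enroll patients into the intervention group". There are no concurrent controls and no switching back.

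Section 13.0 compares delirium incidence by a chi-square test and multivariable logistic regression. It adds: "A sensitivity analysis will be performed in order to assess the possible confounding effect of the non-randomized nature of our study design". The method is a propensity score for standard care versus psychiatric involvement, used for inverse probability weighting, in order to "approximate a balanced covariate distribution between the 2 groups as that would be expected by randomization". The propensity covariates are not named.

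The variables listed in Sections 3.0 and 12 are patient-level: demographics, diagnosis, comorbidity, SOFA score, medications and days from ICU admission to enrolment. Neither list contains calendar date, study week or any unit-level measure, and no analysis over time is planned.

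Section 13.0 treats the between-group difference as the size of the effect of introducing psychiatry, and says that it will inform the design of later, larger trials.

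**The concern.** In this study the lack of randomisation consists of sequential allocation: whoever enrols before the switch is a control, and whoever enrols after it is an intervention patient. The confounding peculiar to that arrangement is change over time in the unit. Staffing, season, bundle adherence or the way CAM-ICU is applied may differ between phases for reasons unrelated to psychiatry. The sensitivity analysis is introduced as the assessment of confounding from the non-randomised design, but its inputs describe patients and not the period in which they were treated.

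The weighted and unweighted results could therefore agree, and be read as reassurance, while part or all of the difference is secular change. That difference would then enter the planning of the definitive trial as an effect size. If favourable drift inflated it, the next trial would be too small. If adverse drift masked a benefit, a useful intervention might be dropped.

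**Working it through.** **Inputs from Section 13.0.** Base incidence: "the incidence of delirium over the past year was roughly 40" per cent. Effect: "a large intervention effect would be on the order of 25% reduction in incident delirium". Evaluable patients: 47 per group. Stated 95% intervals: 8%-42% for the difference and 26%-55% for the base rate. **Assumption.** The size of any drift is not in the documents, so a range is shown.

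**1. The plan's own figures.** Reading the 25% as percentage points (40% to 15%):

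- SE = sqrt(0.40×0.60/47 + 0.15×0.85/47) = 0.0884
- 0.25 ± 1.96×0.0884 = 7.7% to 42.3%, which matches 8%-42%.

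A relative 25% reduction (40% to 30%) would give -9.2% to 29.2%, which does not match. An exact interval around 40% of 47 gives 26.0% to 55.3%, which matches the base-rate interval. The figures reproduce, and they cover sampling error only.

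**2. False signal from drift alone.** Assume no psychiatry effect, 40% in the control phase and 40% minus the drift in the intervention phase. Exact binomial enumeration of the uncorrected chi-square test (two-sided 5%), counting significant results that favour the intervention, 47 per group:

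| Assumed fall between phases | Probability of a significant reduction |
|---|---|
| 0 points | 2.4% |
| 5 points | 7.0% |
| 10 points | 17.1% |
| 15 points | 34.5% |

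**3. Masking by drift the other way.** With a true 25-point effect and no drift, the same test is significant 79% of the time. A 10-point rise unrelated to psychiatry leaves an expected 40% versus 25%. That is the last row of the table, so the chance falls to about 35%.

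**4. The planned result under assumed drift.** Adjusted difference = 25 - d, with 95% limits 25 - d ± 17.3 points, where d is the decline unrelated to psychiatry.

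| d (points) | Difference | 95% CI |
|---|---|---|
| -10 | 35% | 17.7% to 52.3% |
| -5 | 30% | 12.7% to 47.3% |
| 0 | 25% | 7.7% to 42.3% |
| 5 | 20% | 2.7% to 37.3% |
| 10 | 15% | -2.3% to 32.3% |
| 15 | 10% | -7.3% to 27.3% |
| 25 | 0% | -17.3% to 17.3% |

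The lower limit reaches zero at d = 25 - 17.3 = 7.7 points.

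**5. What the weighting does.** Simulation with 52 per group, 3,000 runs, no psychiatry effect, and one measured covariate whose mean shifts between phases (an assumed 0.4 SD shift and log odds ratio 0.5 per SD). Without drift, the raw difference is +4.7 points and the weighted one +0.2, so the case-mix bias is removed. With a 10-point fall added, the weighted difference is -10.1 points, so the whole drift remains.

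**6. Time in the propensity model.** With enrolment order as a covariate, controls occupy positions 1-52 and intervention patients 53-104. The logistic model separates perfectly, fitted scores are essentially 0 or 1, and usable weights do not exist.

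**7. Time in the outcome model.** For evenly spaced enrolment, phase and linear time correlate at sqrt(3)/2 = 0.866. Variance inflation is 1/(1 - 0.75) = 4, so the standard error doubles. In simulation, power for 40% versus 15% falls from 79% to about 24-27%. A 10-point linear drift makes the time term significant in only 8% of runs. A 10-point step at the switch stays wholly in the phase term (median log odds ratio -0.43; 30% against 40% is -0.44).

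**The case against.** Several stronger readings are tempting, and the documents do not support them.

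- *The propensity score is the only adjustment.* It is not: Section 13.0 also plans multivariable logistic regression. That shares the same limit, since it too can use measured covariates only.
- *The plan claims that weighting is equivalent to randomisation.* The phrase "approximate a balanced covariate distribution between the 2 groups as that would be expected by randomization" speaks of covariate balance. It does not claim balance on time or on unmeasured factors. What the section lacks is a statement of that limit.
- *No check over time could be done.* Section 12 gives a list that need not be exhaustive, and days from ICU admission to enrolment cannot be derived without knowing when each patient enrolled. Dates are probably recoverable. They are not listed, and no analysis uses them.
- *Calendar time is the main confounder, or drift has occurred.* Both would be judgement. The documents give no phase durations, trend data or planned co-intervention. A 15-point fall would be 37.5% of the base rate, which is large for consecutive phases.
- *The plan ignores every source of drift.* The bundle is standard care in both phases and CAM-ICU timing is the same in both. Section 12 also records "deliriogenic medications used during study enrollment", which captures some change in practice. Bundle adherence, staffing and season remain uncovered.

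The strongest point against concern is that the study calls itself a pilot, sizes itself on interval width, acknowledges possible confounding and leaves definitive inference to a likely cluster randomised trial. This softens the consequence. It does not remove it, because the pilot's effect size is meant to feed that trial, and a significance test of the primary outcome is still planned.

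**Conclusion.** The concern holds in a bounded form. Group is a deterministic function of enrolment date, so the regression and the weighting can address measured patient case mix, including case mix that shifts over time, and nothing else that changed between phases. The weighting is worth keeping, but it cannot carry out the whole of the assessment that Section 13.0 assigns to it.

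The logical point needs no assumption about drift. Its size does: the 7%, 17% and 35% figures assume falls of 5, 10 and 15 points from 40%, no psychiatry effect and 47 per group. No single corrected estimate exists, because this design cannot estimate the drift. The 7.7-point threshold applies to the planned 40% versus 15% result and must be recalculated on the observed data.

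**What to change.** No redesign is needed.

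(a) Add enrolment date to the Section 12 list, or study week if dates count as identifiers under that section's rule against them.

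(b) In Section 13.0, state that the multivariable regression and the propensity weighting address measured baseline case mix only and do not address calendar time.

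(c) Describe the result, both in the conclusion and when planning the next trial, as a between-phase difference that may include secular change.

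(d) Pre-specify a plot of delirium incidence by enrolment time within each phase, and a drift-bounding table giving the observed difference and its 95% CI under assumed drifts in both directions, laid out as in step 4 of the working.

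A logistic model with phase plus linear time should be exploratory at most. Its standard error roughly doubles, its power for the planned effect is about 24-27%, and it cannot detect a step change at the switch, so neither a null nor a reassuring result from it would mean much.

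The cost is one data field, one figure, one table and a few sentences, together with a more modest headline claim.

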## **1.0 BACKGROUND AND HYPOTHESIS**

We are interested in evaluating a multifaceted prevention protocol for ICU delirium. Delirium affects 45-80% of elderly ICU patients, 60-80% of mechanically ventilated ICU patients, and 20-50% of non-mechanically ventilated ICU patients (1-4). About 30-40% of cases are preventable (1, 2). Without routine screening, delirium is often undiagnosed (5-7). Numerous studies have consistently shown that ICU delirium is associated with a worse prognosis (8). The annual cost of delirium and its ramifications in the U.S., is estimated to be \$4-16 billion (1).

Delirium impacts emotional well-being, as delirious patients experienced delusional memories and had less factual recall than non-delirious patients (9-11). A meta-analysis performed by Zhang et al. found delirium to be associated with a higher mortality rate, longer ICU and hospital lengths of stay, longer duration of mechanical ventilation, and higher probability of discharge to a skilled placement facility. (9) ICU-acquired delirium is independently associated with increased cognitive and physical impairment and health care costs (6, 12). Delirium was also found to be associated with more complications (9,13). Patients who develop delirium have a 2-3 times increased risk of dying during ICU admission (8, 14), with ICU mortality ranging from 1-16% (15-17), and an in-hospital mortality rate of 25% to 33%. (12, 18). It is also associated with increased hospital length of stay (13, 19) and each additional day of delirium increases post-discharge mortality up to a year after discharge (14, 16, 19).

Patients with ICU delirium had a higher incidence of cognitive impairment at hospital discharge, and up to 18 months post-discharge (20, 21) A longer duration of delirium in the hospital was associated with worse global cognition and executive function scores at 3 and 12 months (22), and it is associated with the development of new-onset dementia, or worsening of existing dementia (2, 22). In addition to cognitive problems, delirium was found to be associated with more problems in activities of daily living and worse scores on sensorimotor function tests at follow-up (3). Anxiety, depression, and posttraumatic stress disorder are common in survivors of critical illness (20, 21).

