## **2.0 OBJECTIVES AND PURPOSE**

The purpose of our study is to determine the effect of delirium prevention care bundle protocols, and a multi-disciplinary care model rounding with a psychiatry team (intervention group) on ICU delirium and patient outcomes as compared to a group undergoing standard care without routine psychiatry team participating in ICU rounds (control group). Since the incidence of ICU delirium is so high and it has negative ramifications on patient survival, long-term outcomes, cognitive function, and places a heavy burden on the healthcare system and cost, preventative strategies are desperately needed. Using bundle care protocols and multidisciplinary rounding with psychiatry may be a feasible and cheap measure to help prevent delirium in ICU patients.

The primary objective is the incidence of ICU delirium.

The secondary objectives are:

- duration of delirium
- ICU and hospital length of stay
- days of mechanical ventilation (if applicable)
- in-hospital mortality

Our primary hypothesis is that the intervention of psychiatry team participation in multidisciplinary ICU rounds with the surgical ICU team will result in a decreased incidence of delirium compared to standard care without routine psychiatry team involvement. Our secondary hypothesis is that psychiatric team participation in multidisciplinary ICU rounds will decrease delirium duration, decrease ICU and hospital length of stay, decrease mechanical ventilation duration, and decrease in-hospital mortality compared to the standard care group.

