Additionally, we will collect the following data: age, gender, body mass index, history of alcohol or substance abuse, admitting diagnosis, dementia, comorbid conditions, admitting Sequential Organ Failure Assessment (SOFA) score, deliriogenic medications used during study enrollment, the interventions/medications used to treat delirium as designated by psychiatry and the ICU team (in intervention group) and the ICU team (control group), and the number of days from ICU admission to study enrollment. We will input data into a secure, password protected, encrypted, electronic database, RedCap.

The data points will be compared between the control and intervention groups (see section 13.0).

Our primary outcome is: incidence of ICU delirium.

The secondary outcomes are: duration of delirium/mechanical ventilation, in-house mortality, and hospital and ICU length of stay.

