#### **5.0 SELECTION AND WITHDRAWAL OF SUBJECTS**

Inclusion criteria are:

1. Patients who are  $\geq 18$  years of age
2. Patients admitted to the surgical ICU for  $>48$  hours OR
3. Patients admitted to the ICU  $<24$  hours who have been in the hospital  $>48$  hours OR
4. Patients who return to the ICU after being discharged from the ICU to the floor due a complication or need for higher acuity care.
5. Patients admitted to any surgical service who are receiving care in the 7 West surgical ICU, who are either medically or conservatively managed (non-surgical) or surgically managed as part of their care

Exclusion criteria are:

1. Patients in whom CAM-ICU cannot be performed (severe dementia, stroke or other neurological condition, encephalopathy, mental retardation, severe psychiatric disorder, vegetative state, severe traumatic brain injury, deaf/blind, etc.)
2. Patients who don't speak or understand English
3. Current alcohol or substance abuse
4. Patients who already have delirium within 24-48 hours of their ICU admission [Defined as a positive CAM-ICU test, or based on the *Diagnostic and Statistical Manual of Mental Disorders, Fifth Edition (DSM-V)* diagnostic criteria:

- Disturbance in attention (ie, reduced ability to direct, focus, sustain, and shift attention) and awareness.
- Change in cognition (eg, memory deficit, disorientation, language disturbance, perceptual disturbance) that is not better accounted for by a preexisting, established, or evolving dementia.
- The disturbance develops over a short period (usually hours to days) and tends to fluctuate during the course of the day.

- There is evidence from the history, physical examination, or laboratory findings that the disturbance is caused by a direct physiologic consequence of a general medical condition, an intoxicating substance, medication use, or more than one cause.]

Patients will be screened for eligibility on rounds daily. Patients may withdraw from the study at any point without impacting their healthcare.

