## **9.0 CLINICAL AND LABORATORY EVALUATIONS AND STUDY CALENDAR**

We will collect basic demographic data and screen for delirium using the CAM-ICU (which is standard practice in the ICU). The ABCDEF bundle and CAM-ICU screening tool are performed by the ICU nurses on a daily basis in the morning. The CAM-ICU may be performed later on in the day if the patient's mental status changes. The findings in the ABCDEF bundle and CAM-ICU screening tool are communicated to the ICU team on morning rounds. In patients who develop delirium, we will

collect data on their total ICU/hospital LOS (length of stay), days on mechanical ventilation (if applicable), duration of delirium, and in-hospital mortality.

No additional laboratory studies or investigative studies will be performed for the study.

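### Ventilation status at enrolment is not on the data lists, so the planned adjustment of a before-after comparison can reach it only through admission-time proxies (minor, cheap to fix)

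*Combined protocol and SAP*

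**What the plan says.** Section 3 enrols the control group first and the intervention group afterwards, without randomisation. On the control phase it says: "Enrollment and data collection will continue for as long as it takes to reach the target sample size of 52 patients for this group". The second phase likewise runs until 52 patients are reached.

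Section 13 compares delirium incidence by chi-square test and multivariable logistic regression. It then adds a sensitivity analysis for the lack of randomisation: "A propensity score model for receipt of standard care vs. psychiatric involvement will be performed in order to approximate a balanced covariate distribution". The resulting scores are used for an inverse probability weighted comparison. No covariate is named for either model.

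The Background states that delirium affects "60-80% of mechanically ventilated ICU patients, and 20-50% of non-mechanically ventilated ICU patients". Section 3 makes clear that ventilated patients can be enrolled: "The CAM-ICU can be performed in intubated patients by asking the patient to follow commands with their hands".

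The baseline items in Section 3 are "age, gender, body mass index, history of alcohol or substance abuse, admitting diagnosis, dementia, comorbid conditions, admitting Sequential Organ Failure Assessment (SOFA) score", plus the number of days from ICU admission to enrolment. The list also has deliriogenic drugs used during the study and the treatments given for delirium. Section 12 repeats it. Ventilation appears in both sections only as a duration. Section 2 makes that duration a secondary outcome; the hypothesis is that the intervention will "decrease mechanical ventilation duration, and decrease in-hospital mortality compared to the standard care group".

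Section 9 words outcome collection differently. For patients who become delirious, the team will "collect data on their total ICU/hospital LOS (length of stay), days on mechanical ventilation (if applicable"), along with delirium duration and in-hospital mortality. Sections 3 and 12 carry no such restriction.

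**The concern.** With sequential groups, a change in case mix between phases is mixed with the effect of the intervention. Regression and weighting directly balance only the variables that are recorded and entered. The Background's own ranges, which do not overlap, mark ventilation as a predictor of the primary outcome, but the field that would let the models use it is not listed.

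The listed items fill the gap only in part:

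- Ventilation duration accrues after enrolment and is something the intervention is expected to change. Adjusting for it could remove part of the effect, and it does not show who was ventilated at entry.
- Admitting SOFA and admitting diagnosis are fixed at admission. Enrolment can be later: one eligibility route in Section 5 requires more than 48 hours in the ICU.

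If the ventilated share differed between phases, part of that difference could appear as an intervention effect or hide one. Section 13 intends the effect estimate to inform the design of a larger trial.

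**Working it through.** **Inputs from the documents.** Delirium 60-80% if ventilated and 20-50% if not (Section 1); control incidence about 40%, a reduction of 25%, 47 evaluable per group, and a 95% interval of 8%-42% (Section 13). The documents give no ventilated share and no change in it between phases, so the differences in share below are assumptions.

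**1. The plan's own interval.** Reading the reduction as 25 percentage points (40% to 15%):

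- Half-width = 1.96 × sqrt(0.40×0.60/47 + 0.15×0.85/47) = 0.173.
- Interval = 25 ± 17.3 = 7.7 to 42.3 points, which reproduces 8%-42%.
- A relative reduction (40% to 30%) would give about -9 to 29 points and does not match.

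**2. Ventilated share implied at the midpoints.** With rates of 70% and 35% and 40% overall: (0.40 - 0.35)/(0.70 - 0.35) = 14.3%, or about 7 of 52 patients.

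**3. Movement of the crude difference.** Movement = (difference in ventilated share) × (ventilated rate - non-ventilated rate).

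| Assumed difference in share | Contrast in rates | Movement |
|---|---|---|
| 5 points | 35 (midpoints) | 1.75 points |
| 10 points | 35 (midpoints) | 3.5 points |
| 10 points | 10 (60% vs 50%) | 1 point |
| 10 points | 60 (80% vs 20%) | 6 points |

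The 1-point end pairs two rates that both exceed 40%, so it cannot coexist with the stated control incidence. For a 10-point fall, the control share must be at least 10%. With a ventilated rate of 60%, the non-ventilated rate is then at most (0.40 - 0.06)/0.90 = 37.8%. The contrast is at least 22.2 points and the movement at least 2.2 points.

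These are movements before any adjustment. What the proxies would remove is unknown. The movement may go in either direction.

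**4. Sensitivity to the scale of the effect.** The table applies the same contrast in both phases. If the intervention instead acted proportionally (15/40 = 0.375, also an assumption), the contrast in the intervention phase would be 0.375 × 35 = 13.1 points. A 10-point difference in share would then move that phase's rate by about 1.3 points.

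**5. Room for the extra covariate.** Expected events = 47 × (0.40 + 0.15) = 25.9. Four coefficients (group, ventilation, age, SOFA) leave 25.9/4 = 6.5 events each.

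**The case against.** The strongest reply is that the effect is small and uncertain. At a 14% share, a 10-point fall means going from about 7 to about 2 ventilated patients, and the documents give no evidence of a change in case mix. The Background rates are broad literature ranges, whereas Section 5 limits this cohort to patients in whom CAM-ICU can be done and excludes "Patients who already have delirium within 24-48 hours of their ICU admission". All of this stands and keeps the point minor. It does not remove it: the interval reflects chance variation, but not a systematic change in case mix between phases.

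A second reply is that the information may be available anyway. Section 12's list is not worded as exhaustive, and if ventilation dates are recorded in order to count days, status at enrolment follows. A reader might infer from the lists that the variable will be lost; the documents do not support that. They support only that it is not listed and that no model names it.

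A third reply is that Section 13 names no covariate at all, so singling out ventilation is a preference. The general gap is real, but age, SOFA and dementia are at least on the lists and can be entered later. Ventilation at enrolment is not on them, and the plan's own Background identifies it as prognostic.

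Finally, the propensity model is only a sensitivity analysis. That is so, but the logistic regression for the primary outcome has the same gap.

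**Conclusion.** The point holds as a minor one. Followed as written, the plan would adjust for ventilation at enrolment only as far as admitting SOFA, admitting diagnosis and the other listed items stand in for it.

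The illustrative size is about 3.5 points at the midpoints for an assumed 10-point difference in share. It rests on that assumption, on the Background rates applying to this cohort, and on an equal contrast in both phases. It is about a fifth of the 17.3-point half-width (3.5/17.3 = 0.20).

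A reader might infer that the pilot's result would be materially biased, or that the next trial would be wrongly sized. The documents do not support either. A sample-size consequence would need an assumed shift, an assumed degree of capture by the proxies and an assumed scale for the effect, and Section 13 says only that the estimates will help design later studies.

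The mismatch between Section 9 and Sections 3 and 12 is separate and textual. Read literally, Section 9 would leave length of stay, ventilation days and mortality uncollected in patients without delirium, and those outcomes could not then be compared between the full groups.

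**What to change.** - In Sections 3 and 12, add a field for mechanical ventilation at enrolment (yes/no), recorded for every patient in both phases.
- In Section 13, name it in the logistic and propensity models, within a short set of pre-enrolment covariates such as age and admitting SOFA. State that drugs and delirium treatments recorded after enrolment do not enter those models.
- Separately, reconcile Section 9 with Sections 3 and 12 so that length of stay, ventilation days and mortality are collected for all patients.

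The cost is one chart field and a few sentences; the sample size does not change. The downside is precision. About 6.5 expected events per coefficient leaves the logistic estimate imprecise, and with a share near 14% there would be only about 13 ventilated patients among 94 (0.143 × 94 = 13.4), so the ventilation term itself would be unstable. The weighted interval may also be slightly wider than the crude one. The adjusted results should be reported with that caution.
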